8.2.3 Serious adverse events (SAEs)

The sponsor will report the SAEs through the web portal ToetsingOnline to the accredited METC that approved the protocol once per 2 months.

A Serious Adverse Event (SAE) is any untoward medical occurrence or effect that:

- **Results in death;**
- **Is life threatening (at the time of the event):** An event that, in the opinion of the investigator, would have resulted in immediately fatality if medical intervention had not been taken. This does not include an event that would have been fatal if it had occurred in a more severe form;
- **Requires hospitalisation or prolongation of existing inpatients' hospitalisation:** An event that results in an admission to the hospital for any length of time or prolongs the subject's hospital stay. An elective hospital admission will not be considered as a SAE.
- **Results in persistent or significant disability or incapacity:** An event that results in an unexpected (by investigators opinion) persistent or significant disability or incapacity;
- **Is a congenital anomaly or birth defect:** An anomaly detected at or after birth, or any anomaly that results in fetal loss;
- **Any other important medical event that did not result in any of the outcomes listed above due to medical or surgical intervention but could have been based upon appropriate judgement by the investigator.**

8.2.4 Deaths

For SAEs with the outcome of death, the date and cause of death will be recorded on the appropriate case report form. Deaths that occur during the protocol that are more likely related to disease progression will be considered as an expected AE.

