7.7 Premature termination of the study

Planned interim analyses will be performed after 1, 2, 3, 4, 5, 6, 7, 8, 9, 10, 15, 20, 25, 50, and 100 inclusions. The interim analyses will only be directed at safety. The trial will be stopped because of any safety issue of the treatment under study, defined as a higher occurrence of SAEs in the treatment than in the control group. There will be no interim analysis for efficacy in this trial, since it is very unlikely that either 'futility' or 'proof beyond reasonable doubt' will be achieved prematurely in this relatively small phase 2 clinical trial.

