8.2 AEs, SAEs and SUSARs

8.2.1 (Serious) Adverse events reporting

As this is a randomised controlled trial with a new drug all (serious) adverse events mentioned in paragraph 8.2.2 and 8.3.3 are required to be reported to the Sponsor and recorded in the electronic database. The sponsor is responsible to report the SAE to the accredited METC that approved the protocol.

Reporting of SAEs will be the responsibility of the study coordinator and the principle investigator. The local principle investigators will report on AEs, SAEs and SUSARs within the relevant time windows mentioned below. A dedicated study nurse will collect all AEs, SAEs, and SUSARs and discuss these with the principle investigator, every week.

Since case fatality in the patient population under study is known to be 50-60%, with most deaths occurring in the first week of ICU admission, line listing of all SAEs including deaths is requested, with reporting to the accredited METC once per two months. Exceptions will be made for (1) the first ten inclusions in the trial, (2) SAEs that are probably related to the trial, and (3) Suspected Unexpected Serious Adverse Reactions, for which expedited reporting will take place.

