Thereafter, the DSMB will perform safety analyses after 15, 20, 25, 50, and 100 inclusions. At that time, the DSMB will review data on SAEs, SUSARs, poor outcomes, and deaths per centre. This information will be sent to the DSMB at one week \pm 3 days after inclusion for the interim analyses at 15, 20, and 25 inclusions. For these interim analysis, the trial will only continue after a positive sign from the DSMB. For the interim analyses at 50 and 100 inclusions, the information will be sent after having reached the secondary outcome measure at three months. In addition, the DSMB will review general aspects of the trial, including patient recruitment, patient inclusion, and unexpected events. Because of the expected high proportion of patients with a poor outcome in the patient group under study, and the consequent overlap between safety endpoints and the primary endpoint, the evaluation of safety by the DSMB will be quantitative and qualitative. In addition, suspected unexpected serious adverse reactions (SUSARs) will be reported <48 hours to the METC.

The composition, tasks and responsibilities of the DSMB are described in K5: DSMB Charter.

The DSMB will advise to stop the trial at the following moments:

- A higher number of SAEs in the treatment than in the control group
- Any SUSARs
- Any other safety issues

The advice(s) of the DSMB will be sent to the Principle Investigator of the study and the METC. Should the Principle Investigator decide not to fully implement the advice of the DSMB, the Principle Investigator will send the advice to the reviewing METC, including a note to substantiate why (part of) the advice of the DSMB will not be followed.

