9.4 Interim analysis (if applicable)

Please also see chapter 7: safety Reporting / DSMB. The trial will be monitored by an independent DSMB. Details on the composition of the DSMB and rules on analysis and reporting are included in K5: "DSMB charter".

The trial will be stopped because of any safety issue of the treatment under study, defined as a higher occurrence of SAEs in the treatment than in the control group, any SUSAR, or any other safety concern. There will be no interim analysis for efficacy in this trial, since we consider it very unlikely that either 'futility' or 'proof beyond reasonable doubt' will be achieved prematurely in this relatively small phase 2 clinical trial.

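### Section 8.2.4 leaves open whether deaths attributed to disease progression stay in the SAE count on which the only numeric stopping criterion rests

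*Protocol*

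**What the plan says.** **Classification of death.** Three sections of the protocol treat every death as an SAE, without exception by cause.

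- Section 8.2.1 states that "line listing of all SAEs including deaths is requested", for two-monthly reporting to the ethics committee.
- Section 8.2.2 lists death, marked as an SAE, among the events that are always reported.
- Section 8.2.3 gives "Results in death" as the first criterion in the definition of an SAE.

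Section 8.2.4 opens by speaking of SAEs with a fatal outcome, for which date and cause are recorded. Its next sentence reads: "Deaths that occur during the protocol that are more likely related to disease progression will be considered as an expected AE".

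**Stopping criterion.** It appears three times.

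- Section 7.7 stops the trial for a safety issue "defined as a higher occurrence of SAEs in the treatment than in the control group".
- Section 8.5 has the DSMB advise stopping for "A higher number of SAEs in the treatment than in the control group", for any SUSAR, or for any other safety issue.
- Section 9.4 gives "higher occurrence of SAEs in the treatment than in the control group, any SUSAR, or any other safety concern".

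None of the three says whether deaths covered by 8.2.4 are counted.

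**Expected mortality.** Section 8.2.1 says that "case fatality in the patient population under study is known to be 50-60" per cent, with most deaths in the first week on the ICU. Section 10.3 says that half of all patients never awaken and die of severe postanoxic encephalopathy.

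**The concern.** The protocol uses AE and SAE as separate classes with separate reporting clocks: under 8.2.2 an AE goes to the principal investigator within 10 working days and an SAE within 24 hours. A site that follows the second sentence of 8.2.4 literally could record a death from postanoxic encephalopathy as an AE. A site that follows 8.2.2 or 8.2.3 would record the same death as an SAE.

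The choice matters because the formal criterion is a comparison of SAE numbers between arms. If ghrelin worsened survival, the extra deaths would probably look like neurological or cardiac deaths, which are the deaths most readily ascribed to the underlying disease. Attribution patient by patient is poorly suited to detecting such an excess; an all-cause count by arm does not depend on attribution. As written, the same data could meet the SAE criterion under one section and miss it under another.

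**Working it through.** **Inputs from the protocol**

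- Sample size 160 (section 4.4), allocated 1:1 (section 7.2).
- Last planned interim look at 100 inclusions (section 7.7), about 50 per arm.
- Case fatality 50-60% (section 8.2.1). No time horizon is given, so applying it at the 100-inclusion look, for which section 8.5 waits for three-month data, is an approximation.
- Deaths from postanoxic encephalopathy: about 50% of all patients (section 10.3).

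The sample size reproduces: a difference of 0.8, SD 1.8, two-sided alpha 0.05 (the protocol does not state sidedness) and 80% power give 80 per arm, 160 in total. This figure is not in dispute; it serves only to convert fatality into deaths.

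**Step 1. Deaths at stake** = number of patients × case fatality.

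- At 100 inclusions: 100 × 0.50 = 50 to 100 × 0.60 = 60.
- In the whole trial: 160 × 0.50 = 80 to 160 × 0.60 = 96.

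The first line is the relevant one, because no interim look is planned after 100 inclusions.

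**Step 2. Share open to relabelling** = proportion of patients dying of postanoxic encephalopathy ÷ case fatality.

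- 0.50 / 0.60 = 83%; 0.50 / 0.50 = 100%.
- At 100 inclusions, about 50 of the 50-60 deaths could be ascribed to disease progression, leaving 0-10 in the SAE count.

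So, on the protocol's own figures, most deaths are affected if 8.2.4 is read literally.

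**Step 3. Effect on the criterion (illustration).** Let deaths be the only events counted, with 50 patients per arm and control fatality of 50%. The ghrelin fatality rates below are assumptions; the protocol gives none. A fraction s of deaths is relabelled and dropped, equally in both arms, so each count is binomial with n = 50 and probability fatality × (1 − s). The entry is the exact probability that the ghrelin count exceeds the control count, P(X_ghrelin > X_control), for independent binomials.

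| Assumed ghrelin fatality | s = 0 (all counted) | s = 0.5 | s = 0.8 | s = 1 |
|---|---|---|---|---|
| 50% (no difference) | 0.46 | 0.45 | 0.43 | 0 |
| 60% | 0.82 | 0.67 | 0.56 | 0 |
| 65% | 0.92 | 0.77 | 0.62 | 0 |
| 70% | 0.98 | 0.84 | 0.68 | 0 |

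Relabelling weakens the mortality signal in the SAE count step by step. It removes the signal altogether only if every death is relabelled. Non-fatal SAEs would also enter the real count, and the protocol gives no rate for them.

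**Step 4. Does the text settle the reading?** It does not. For the expectedness reading: 8.2.4 itself begins from SAEs with a fatal outcome, and the section that follows (8.2.5) treats seriousness and expectedness as separate conditions. For the literal reading: the sentence says AE where SAE was available, and it is not needed to keep these deaths from being SUSARs, since 8.2.5 already requires a degree of probability that the event is a reaction to the product.

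**The case against.** The best defence is that 8.2.4 speaks of expectedness and not of seriousness. It nowhere says that such deaths are non-serious or uncounted. The protocol also uses adverse event as an umbrella term: 8.2.2 lists death, marked as an SAE, among the adverse events that are always reported, so an expected AE can still be serious. On this reading progression deaths are merely not SUSARs and there is no conflict. That reading is plausible, and the authors may well have meant it. But the document does not state it, and the literal reading remains open to a site.

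A reader might go further and infer that the protocol hides mortality from safety monitoring, or that the SAE count is the only quantitative safety comparison. The document supports neither. Under section 8.5 the DSMB receives deaths and poor outcomes as items separate from SAEs, with no filter by cause. For the first ten patients it gets unblinded individual reports. It evaluates safety both quantitatively and qualitatively, and it may advise stopping for any other safety issue; section 9.4 has a matching ground. Case fatality at one week and six months is a secondary outcome (section 7.1.2). An excess of deaths could therefore lead to stopping even if it were missing from the SAE count.

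Finally, sections 8.5 and 9.4 place the rules on analysis and reporting in the DSMB charter, which is not shown and may define the count. This limits the consequence but does not remove the inconsistency: sites classify events from the protocol, and the criterion is stated there three times.

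**Conclusion.** The point holds as an inconsistency in a formal decision criterion. Three sections make every death an SAE, a fourth uses wording that can be read as taking progression deaths out of that class, and the only numeric stopping criterion counts SAEs by arm without saying which applies. At the stated fatality, about 50-60 deaths by the last interim look are concerned, of which about 50 could be ascribed to the underlying disease. This rests on the literal reading of 8.2.4, on the protocol's own fatality figures, and on the charter not already resolving the matter. The probabilities in the table rest in addition on assumed ghrelin fatality rates and on deaths being the only events counted. It is worth correcting because it bears on a safety criterion and takes one sentence.

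**What to change.** Reconcile section 8.2.4 with 8.2.1-8.2.3 by stating that:

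- every death remains an SAE and is counted by arm in each DSMB comparison, whatever its presumed cause;
- the term expected bears only on SUSAR and expedited reporting;
- all-cause deaths by arm are shown as a line separate from other SAEs.

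Align the DSMB charter with this wording.

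The cost is a short protocol amendment and a charter check. SAE listings may become longer, although the two-monthly line listing in 8.2.1 already covers deaths. The by-arm SAE count will be dominated by deaths, which is why the separate line is needed. Counting all deaths also makes plain that the criterion has no margin: with equal fatality of 50% and 50 patients per arm, the ghrelin count is the higher one with probability 0.46. That is a separate matter, which this change neither causes nor resolves.

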8.2.5 Suspected unexpected serious adverse reactions (SUSARs)

Adverse reactions are all untoward and unintended responses to an investigational product related to any dose administered.

Unexpected adverse reactions are SUSARs if the following three conditions are met:

1. the event must be serious (see chapter 8.2.3);
2. there must be a certain degree of probability that the event is a harmful and an undesirable reaction to the medicinal product under investigation, regardless of the administered dose;
3. the adverse reaction must be unexpected, that is to say, the nature and severity of the adverse reaction are not in agreement with the product information as recorded in:
 - Investigational Medicinal Product Dossier (IMPD); Investigator's Brochure for an unauthorised medicinal product.

The Principle Investigator will report expedited the following SUSARs through the web portal *ToetsingOnline* to the METC:

- SUSARs that have arisen in the clinical trial that was assessed by the METC;
- SUSARs that have arisen in other clinical trials of the same Principle Investigator and with the same medicinal product, and that could have consequences for the safety of the subjects involved in the clinical trial that was assessed by the METC.

The expedited reporting of SUSARs through the web portal Eudravigilance or *ToetsingOnline* is sufficient as notification to the competent authority.

The Principle Investigator will report expedited all SUSARs to the competent authorities in other Member States, according to the requirements of the Member States.

The expedited reporting will occur not later than 15 days after the Principle Investigator has first knowledge of the adverse reactions. For fatal or life threatening cases the term will be maximal 7 days for a preliminary report with another 8 days for completion of the report.

With any SUSAR, treatment allocation will be 'unblinded'.

8.3 Annual safety report

In addition to the expedited reporting of SUSARs, the Principle Investigator will submit, once a year throughout the clinical trial, a safety report to the accredited METC, competent authority, and competent authorities of the concerned Member States.

This safety report consists of:

- a list of all suspected (unexpected or expected) serious adverse reactions, along with an aggregated summary table of all reported serious adverse reactions, ordered by organ system, per study;
- a report concerning the safety of the subjects, consisting of a complete safety analysis and an evaluation of the balance between the efficacy and the harmfulness of the medicine under investigation.

8.4 Follow-up of adverse events

All AEs will be followed until they have abated, or until a stable situation has been reached. Depending on the event, follow up may require additional tests or medical procedures as indicated, and/or referral to the general physician or a medical specialist.

SAEs need to be reported till end of study within the Netherlands, as defined in the protocol.

8.5 [Data Safety Monitoring Board (DSMB) / Safety Committee]

The trial will be monitored by an independent data monitoring committee. The data monitoring board (DSMB) will consist of Dr. [name] (neurologist UMCU), [name] (intensivist UMCU), Dr. [name] (biostatistician LUMC), and dr. [name] (clinical pharmacologist Apotheek Haagse Ziekenhuizen en Hagaziekenhuis). The first three members of this DSMB are also involved in the TELSTAR trial (www.telstartrial.nl) and know the vulnerable population under study very well. Details on the DSMB and rules on analysis and reporting are included in K5: “DSMB charter”.

The DSMB is established to perform interim analyses for safety. Safety analyses will be performed at an individual patient level for the first ten inclusions in the trial. For these first ten inclusions, the DSMB will receive by email unblinded reports of SAEs, AEs, SUSARs, poor outcomes, and deaths after each individual inclusion. Thereby, the DSMB will have access to individual patient files. The information will be sent to the DSMB at one week \pm 3 days after inclusion (i.e. the duration of treatment). Analysis of safety in these first ten inclusions will be largely qualitative. The first ten patients will be included sequentially in one hospital (MST), where the next inclusion will only take place after a positive sign from the DSMB.

Thereafter, the DSMB will perform safety analyses after 15, 20, 25, 50, and 100 inclusions. At that time, the DSMB will review data on SAEs, SUSARs, poor outcomes, and deaths per centre. This information will be sent to the DSMB at one week \pm 3 days after inclusion for the interim analyses at 15, 20, and 25 inclusions. For these interim analysis, the trial will only continue after a positive sign from the DSMB. For the interim analyses at 50 and 100 inclusions, the information will be sent after having reached the secondary outcome measure at three months. In addition, the DSMB will review general aspects of the trial, including patient recruitment, patient inclusion, and unexpected events. Because of the expected high proportion of patients with a poor outcome in the patient group under study, and the consequent overlap between safety endpoints and the primary endpoint, the evaluation of safety by the DSMB will be quantitative and qualitative. In addition, suspected unexpected serious adverse reactions (SUSARs) will be reported <48 hours to the METC.

The composition, tasks and responsibilities of the DSMB are described in K5: DSMB Charter.

The DSMB will advise to stop the trial at the following moments:

- A higher number of SAEs in the treatment than in the control group
- Any SUSARs
- Any other safety issues

The advice(s) of the DSMB will be sent to the Principle Investigator of the study and the METC. Should the Principle Investigator decide not to fully implement the advice of the DSMB, the Principle Investigator will send the advice to the reviewing METC, including a note to substantiate why (part of) the advice of the DSMB will not be followed.

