4. STUDY POPULATION

4.1 Population (base)

Comatose patients (GCS score of 8 or lower) after cardiac arrest and successful cardiopulmonary resuscitation, admitted to intensive care units of participating hospitals, will be included within 12 hours after return of spontaneous circulation. Informed consent and randomization will have to be obtained within 12 hours after return of spontaneous circulation. The trial treatment will have to be started within three hours after randomization (please see procedure at 7.3).

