6.6 Dosages, dosage modifications and method of administration

Active treatment group:

Acyl ghrelin 600µg in 50cc normal saline, intravenously, twice daily during one week.

The dosage will be modified in patients of less than 60kg to 10µg/kg.

Placebo group:

50cc normal saline

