7.3 Study procedures

All comatose patients after cardiac arrest will be admitted to intensive care units to receive treatment according to guidelines, as described in national and local ICU protocols.

A legal representative or family member of all eligible patients will be informed about the study as soon as possible after admission on the ICU by the ICU staff/research coordinators. Since any beneficial effect of the treatment under study is assumed to be larger with earlier

initiation, randomization and treatment should be initiated within 12 hours after cardiac arrest (ROSC). All participating centers have ample experience with inclusion of patients with acute cardiac arrest or cerebral ischemia in intervention studies.

Patients who are enrolled in this trial will receive intravenous treatment with acylated ghrelin 600micrg twice daily vs. placebo. The duration of the treatment is one week. This treatment duration of one week will be adhered to, both in patients that remain comatose, and in patients that awaken within a week. If patients are transferred from the ICU to a cardiac care unit or general ward within one week, treatment will be continued for a total of one week, as well. Intravenous treatment will be administered through infusion systems that are already in situ in all of these patients. There will be no additional punctures.

Baseline data will be obtained at admission as part of regular patient care and include: clinical data, EEG data, medical history, and use of medication. In addition, a venous blood samples (5cc) will be taken to measure the baseline ghrelin concentration. This sample will be collected during routine blood sampling; there will be no additional punctures.

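### For the first ten sequential inclusions, the minus side of the ±3 day window permits a DSMB report at day 4, before the treatment week it is equated with has ended

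*Protocol*

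**What the plan says.** Section 8.5 sets up a staged safety review. For the opening stage, "Safety analyses will be performed at an individual patient level for the first ten inclusions in the trial". The DSMB gets unblinded reports by email after each of these inclusions and has access to the patient files. The information goes out at one week plus or minus "3 days after inclusion (i.e. the duration of treatment"). The first ten patients are enrolled one after another in a single hospital, "where the next inclusion will only take place after a positive sign from the DSMB".

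On treatment, section 7.3 states "The duration of the treatment is one week", section 6.6 has the study drug given "intravenously, twice daily during one week", and the procedures table in section 7.3 places treatment on days 0 to 6. Section 4.1 adds: "The trial treatment will have to be started within three hours after randomization".

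For the next stage, section 8.5 repeats the timing, one week plus or minus "3 days after inclusion for the interim analyses at 15, 20, and 25 inclusions", this time without equating it to the duration of treatment. It adds: "For these interim analysis, the trial will only continue after a positive sign from the DSMB".

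Sections 8.5 and 9.4 refer to the DSMB charter (K5) for rules on analysis and reporting. The charter is not part of the document at hand.

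**The concern.** The reporting time is tied to the length of treatment, but a two-sided tolerance does not respect that tie. A report sent up to 3 days late still contains the whole treatment week. A report sent up to 3 days early cannot. Since the report feeds the decision to admit the next patient, the early side of the window shortens what has been observed at that decision.

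What is at stake is how much repeat-dose exposure has been seen before another patient is exposed. The protocol's own background makes the later doses informative. Section 6.3 says ghrelin has not been given to comatose patients after cardiac arrest. Section 6.5 gives 3 µg/kg twice daily as the highest regimen tested in humans for a week or more and describes the trial dose as about 7.5 to 10 µg/kg. I cite these figures only to show why the full week matters for the review; I take no view on the dose. The primary endpoint, the sample size and the error rates are not touched.

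**Working it through.** **Inputs**
- Report time: 7 ± 3 days after inclusion (section 8.5).
- Treatment: twice daily for 7 days (sections 6.6 and 7.3), days 0 to 6 in the procedures table.
- First dose: 0 to 3 hours after randomisation (section 4.1). I take inclusion and randomisation as the same moment, since section 7.2 has the pharmacist do both in one step.
- Assumption: doses 12 hours apart. The protocol says only twice daily.

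**Window.** 7 − 3 = day 4 (96 h); 7 + 3 = day 10 (240 h). Length: 6 days.

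**Planned doses.** 2 × 7 = 14.

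**Time of the last dose.** 13 intervals × 12 h = 156 h with a start at 0 h, or 159 h with a start at 3 h, which is day 6.5 to about 6.6.

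**Doses given before the report.** The counts are the same for both start times.

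| Report at | Given | Still to come |
|---|---|---|
| Day 4 (96 h) | 8 | 6/14 = 43% |
| Day 5 (120 h) | 10 | 4/14 = 29% |
| Day 6 (144 h) | 12 | 2/14 = 14% |
| Day 7 (168 h) or later | 14 | 0 |

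**Share of the window before the last dose.** (6.5 − 4)/6 = 42%; (6.625 − 4)/6 = 44%. Share before day 7: (7 − 4)/6 = 50%.

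**Patients on ghrelin among the first ten.** Section 7.2 specifies 1:1 randomisation in blocks of 10 stratified by site, and section 8.5 places all ten at one site. One complete block gives 10/2 = 5. I say about five, because withdrawals are replaced (section 7.5).

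**Looks at 15, 20 and 25 inclusions.** These are cumulative. If only the latest patient is still on treatment (an assumption) and the report goes out at day 4, 6 planned doses are unobserved:
- 15 patients: 6/(15 × 14) = 6/210 = 2.9%
- 20 patients: 6/(20 × 14) = 6/280 = 2.1%
- 25 patients: 6/(25 × 14) = 6/350 = 1.7%

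Faster enrolment, with several patients on treatment at once, would raise these shares.

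**The case against.** The strongest reply is that the bracketed remark explains only why the nominal time is one week. A tolerance around a nominal time is ordinary scheduling language and does not promise that every report contains a finished course. Moreover, the window governs when information is sent, and the positive sign is a separate act: the DSMB sees unblinded data, can open the files and can wait. The charter may require it to. Nor are later events lost. Serious adverse events reach the principal investigator within 24 hours (section 8.2.2), the first ten inclusions are excepted from two-monthly reporting to the ethics committee (section 8.2.1), and any SUSAR leads the DSMB to advise stopping (section 8.5).

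Much of this stands, and it rules out three stronger readings that a reader might infer:
- *That release at day 4 is planned.* The text allows it and does not call for it.
- *That all ten reviews can miss ghrelin exposure.* About five patients receive placebo.
- *That the same contradiction, with 29 to 43% of exposure missing, recurs at 15, 20 and 25.* The sentence on those looks does not mention the duration of treatment, so there is no stated basis to contradict, and a per-patient share does not carry over to a cumulative review.

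What does not stand is that the other channels close the gap. None of them makes the next inclusion wait for the treatment week to finish. Even on the scheduling reading, only a late tolerance is harmless to what the report contains; an early one removes part of the week. If the charter does set a minimum, the protocol sentence should still be brought into line with it.

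**Conclusion.** The point holds, as a minor one, for the first ten sequential inclusions. A report that complies with section 8.5 can go to the DSMB at day 4, with 8 of 14 planned doses given and 43% still to come (29% at day 5), and the protocol sets no minimum observation time before the positive sign. Some 42 to 44% of the permitted window lies before the last dose; a report from day 7 onward covers the full course.

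The dose counts rest on 12-hour spacing and on a first dose within 3 hours of inclusion. The practical consequence depends on whether the DSMB would act on an early report and on what the unseen charter says; neither can be judged from the protocol. For the looks at 15, 20 and 25, the case is one of consistency only, with about 2 to 3% of cumulative planned doses unobserved under the assumption stated above.

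**What to change.** In section 8.5, reconcile the window for the first ten inclusions with its stated basis by making it one-sided: data are sent 0 to 3 days after the one-week treatment period ends. Align the DSMB charter. The same wording can be used for the looks at 15, 20 and 25 inclusions, for consistency.

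The cost is a wording change plus some time. Compared with the earliest report now permitted, each step lengthens by at most 3 days: 9 gaps between ten patients × 3 = 27 days, or 10 × 3 = 30 days if the release after the tenth patient is counted. The latest permitted report stays at day 10. Treatment, sample size and analysis are unchanged.
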